### **3.6 Estimated Study Duration**

Each subject's study duration may be up to 26 months, consisting of a Screening Phase (1 month), a Treatment and Assessment Phase (1 months) that includes 12 months of treatment, the initial end-of-study (EOS) Visit 30 ( $\pm 5$ ) days after the last dose and the confirmatory EOS visit 1 month later, and the Open-label

Extension (OLE) Phase during which subjects will receive active treatment with NEOD001 for 12 months and may receive concurrent chemotherapy.

The 13-month Treatment and Assessment Phase is the active study period.

During the OLE study, subjects will be seen monthly, and local and central laboratory testing for the OLE study will be obtained and collected every 3 months. The OLE study will continue until the last subject enrolled on study completes study participation.

### **3.7 Definition of End of Study**

The study will end when the last subject treated with NEOD001 or placebo completes either the ETD visit or the active study period and, if eligible, the 12 months on the OLE study after the confirmatory EOS visit.

## **4.0 SELECTION, DISCONTINUATION, AND WITHDRAWAL OF SUBJECTS**

### **4.1 Inclusion Criteria**

Subjects must meet **all** of the following criteria:

1. 18 years of age or older
2. Biopsy-proven diagnosis of AL amyloidosis by immunohistochemistry or mass spectroscopy of a tissue biopsy excluding bone marrow
3. Screening renal biopsy for RAIN confirming AL amyloidosis as exclusive or dominant cause of renal damage
4. Persistent renal involvement with proteinuria (predominantly albumin) > 500mg/day in a 24-hour urine collection
5. CKD 1, 2 or 3
6. ≥1 prior systemic hematologic therapy for free light chain (FLC) producing hematologic malignancy underlying the initial diagnosis of AL amyloidosis with a FLC response to treatment (PR, VGPR, CR) that is deemed stable and not requiring further treatment
7. ECOG Performance Status ≤ 2
8. Clinical laboratory values:
  - Absolute neutrophil count > 1000/µL
  - Platelet count > 75,000/µL
  - Total bilirubin ≤ 1.5X ULN
  - Alkaline phosphatase ≤ 5X ULN
  - ALT or AST ≤ 3X ULN
  - NT-proBNP < 1800 pg/mL
9. Voluntary written consent must be given before performance of any study-related procedure not part of standard medical care with the understanding that consent may be withdrawn by the patient at any time without prejudice to future medical care.

## 4.2 Exclusion Criteria

Subjects must **not meet any** of the following criteria:

1. Amyloidosis due to mutations of the transthyretin gene or presence of other non-AL amyloidosis
2. Female patients who are lactating, breastfeeding, or pregnant. Men and women of childbearing potential need to use birth control while participating in the study.
3. Patients who have received chemotherapy within 6 months, or SCT within 12 months, for the light-chain producing hematologic disease causing AL amyloidosis, at the time of the first dose of NEOD001 (month 1 day 1)
5. Patients who at initial diagnosis or later met the International Myeloma Working Group (IMWG) definition of active multiple myeloma (Appendix 3)
6. Medically documented cardiac syncope, uncompensated congestive heart failure, myocardial infarction within the previous 6 months, unstable angina pectoris, clinically significant repetitive atrial or ventricular arrhythmias despite antiarrhythmic treatment, or severe orthostatic hypotension or clinically significant uncompensated autonomic insufficiency.
7. Comorbid systemic illnesses or other severe concurrent disease which, in the judgment of the investigator, would make the patient inappropriate for entry into this study or interfere significantly with the proper assessment of safety and toxicity of the prescribed regimens.
8. Ongoing or active infection, known HIV positive, known to be hepatitis B surface antigen-positive or has known or suspected active hepatitis C infection.
9. Psychiatric illness/social situations that would limit compliance with study requirements. This will not be assessed for the study. Patients in active care that limits their ability to come to the center for therapy or patients with family situations that limit their ability to come to the center for therapy will not be eligible because they will not be able to comply with study requirements.

## 4.3 Early Treatment Discontinuation

If the subject discontinues study drug prior to the initial EOS visit, the subject should return for an ETD Visit 30 ( $\pm 5$ ) days after their final administration of study drug as per Section 6.2. If a subject fails to return for the scheduled visit, a documented effort must be made to determine the reason. If the subject cannot be reached by telephone after 2 attempts, a certified letter will be sent to the subject (or the subject's legally authorized representative, if appropriate) requesting contact with the Investigator. This letter will be submitted to the IRB for review prior to use. This information will be recorded in the study records.

If the subject discontinues study drug prior to initial EOS visit, but is willing to continue to participate in study visits, continue to collect data through the ETD Visit (i.e., 30 [ $\pm 5$ ] days after their final administration of study drug). Following the ETD Visit, subsequent clinic evaluations will be standard-of-care visits with testing as clinically warranted, usually at a minimum of every 3 months. Testing in this circumstance can be performed at a distance. Every effort should be made for the subject to return to the clinic at the month 12 time point for completion of all of the initial EOS visit assessments.

Reasons for early discontinuation from study drug treatment may include, but are not limited to:

- Hematologic progression requiring immediate initiation of chemotherapy; the chemotherapy regimen should be documented on the appropriate case report form.
- Need for organ transplant or major surgery.
- Occurrence of an AE or clinically significant laboratory abnormality that, in the opinion of the Investigator, warrants the subject's permanent discontinuation from study drug treatment; the Medical Monitor ([name]) should be notified as soon as possible of any discontinuation of study drug due to an AE.
- Suspected or confirmed pregnancy or nursing during study treatment period. Female subjects whose pregnancy test is positive at the ETD visit must be followed to term or until termination of the pregnancy.

#### **4.4 Early Termination from the Study**

Early termination occurs if the subject fails to complete the entire study, through the confirmatory EOS visit and 12-month period after the confirmatory EOS visit. Subjects may withdraw their consent to participate in this study at any time without prejudice. The Investigator must withdraw from the study any subject who requests to be withdrawn. A subject's participation in the study may be discontinued at any time at the discretion of the Investigator in accordance with his/her clinical judgment. The Sponsor (Tufts) or its designee should be notified in a timely manner of all subject discontinuations. When possible, the tests and evaluations listed for the ETD Visit should be carried out.

Early termination from the study may occur if:

- In the opinion of the Investigator, the subject cannot safely participate in the procedures required by the protocol
- Subject withdraws consent
- Subject is unwilling or unable to comply with the study requirements
- Subject is lost to follow-up

The Sponsor, (Tufts Medical Center) and the Prothena Therapeutics Limited who is funding the study reserve the right to discontinue the study at any time for any reason, including but not limited to, clinical or administrative reasons, or to discontinue participation of an individual Investigator or site for any reason, including but not limited to, poor enrollment or noncompliance. At any point in the study, if the subject is unwilling to return to the clinic for further visits but is willing to discuss their health status by phone, follow-up phone calls should be made to the subject or their caregiver every 3 months.

Vital status will be collected within legal and ethical boundaries for all randomized subjects receiving at least one dose of study drug and will be searched in public sources. During the study close-out period, at completion of the last subject's participation in the OLE, survival status will be collected within legal and ethical boundaries for all randomized subjects who withdrew participation from the main or OLE study. If vital status is determined, the subject will not be considered lost to follow-up.

#### **4.5 Replacement of Subjects**

Randomized subjects who do not begin month 1 day 1 treatment with NEOD001 or placebo may be replaced. Randomized subjects who have received treatment and drop out of the study for any reason will not be replaced.

## **4.6 Termination of the Clinical Study**

If the Investigator, the Sponsor (Tufts) or the Medical Monitor becomes aware of conditions or events that suggest a possible hazard to subjects if the clinical study continues, then the clinical study may be terminated. The clinical study may also be terminated at the Sponsor's discretion in the absence of such a finding, at any time and for any reason.

Conditions that may warrant termination of the clinical study include, but are not limited to:

- The discovery of an unexpected, relevant, or unacceptable risk to the subjects enrolled in the clinical study
- A decision by the Sponsor (Tufts) to suspend the study, or to suspend administration of the study drug, for any reason

## **4.7 Local Recruitment Methods**

All other sites will follow their own recruitment methods per their SOPs. Tufts Medical Center will follow the following methods:

1. Who will identify potential study subjects: The Principal Investigator, Co-Investigators, and Study Nurse Coordinator will work together to identify potential study subjects
2. Describe how subjects will be identified (e.g., medical record screening, approached in clinic): Study subjects will be identified through new patient intake forms, during tumor board reviews, at clinic visits, by patient self-referral, (e.g. as contacting the study coordinator directly from the contact information on a website) and by physician referrals. If a patient (potential study participant) contacts the study nurse/coordinator by calling the telephone number or responding to other contact information on a website posting / advertisement for a particular study, the following information will be obtained from the potential study participant: name, telephone number, diagnosis, and medical history (medical history includes a brief description of the treatment he/she has received to date). The study nurse/coordinator will provide information about the study (limited to the information in the ICF and website posting) and the potential study participant will be advised to schedule an appointment with the PI or a Co-I (study doctor) to evaluate eligibility. Upon request, the study nurse can provide the consent form via mail or e-mail. Potential study participants will be advised to call the study nurse/coordinator with any questions they have about the consent form.
3. Who will approach subjects or their legally authorized representative about participation: The Principal Investigator, Co-Investigator or study nurse, at the request of the PI or Co-I, will approach subjects about participation.
4. When will subjects or their legally authorized representative be approached about participation: Potential subjects will be approached during their clinic visits.
5. How will subjects or their legally authorized representative be approached about participation: During the course of a clinic visit, the patient will be given all the various options for the treatment for their disease. All standard treatment options will be discussed along with any clinical trials that the patient may be eligible for. The risks and possible benefits will be presented and discussed with the patient by the study investigator or by their physician. If the patient demonstrates an interest in participating in a particular clinical trial, the specific study procedures will be more thoroughly reviewed with the patient and he/she will be given a copy of the Informed Consent Form to take home and to read about. For further detail about the consent process, see Section I.

## 5. TREATMENT OF SUBJECTS

### 5.1 Study Drug

#### 5.1.1 Formulation, Packaging, and Labeling

The active study drug, NEOD001, is supplied as a sterile, lyophilized dosage form in a 20/25 mL vial containing 500 mg/vial NEOD001. After reconstitution with 9.6 mL of sterile water for injection (WFI), the vial will contain 50 mg/mL of NEOD001, 17.5 mM L-Histidine, 7.5 mM L-Histidine Hydrochloride monohydrate, 230 mM Trehalose dehydrate, 0.02% Polysorbate 20.

At a minimum, the label for each vial shipped to a clinical site will provide the following information: batch number/lot number, required storage conditions, directions for use, and any region-specific caution statements, e.g., "New Drug -Limited by United States Federal Law to Investigational Use." 5.1.2 Shipping, Storage, and Handling

NEOD001 will be shipped to clinical sites in individual cartons (one vial per carton). Upon receipt, a study staff member will place the study drug in a refrigerator at a temperature ranging from 2°C to 8°C in a secure, locked location. Access to the study drug should be strictly limited to the study staff. Neither the Investigator nor any member of the study staff will distribute any of the study supplies to any person who is not participating in this study.

If a study staff member becomes aware that the study drug has not been properly handled (i.e., supply arrived at room temperature or was not placed in refrigerator upon receipt), the Sponsor or its designee must be contacted immediately. In such an event, study drug should be quarantined in a 2°C to 8°C refrigerator and must not be administered to any subject until the Sponsor or its designee provides further direction.

It is expected that the site staff will maintain refrigerator temperature logs in the investigational product storage area, recording the temperature at least once each working day.

See Section 5.2 and the Pharmacy Manual for further details about shipping, storage and handling of NEOD001.

#### 5.1.2 Accountability and Return of Study Supplies

The study drug will be dispensed at the discretion of the Investigator under the direction of the Unblinded Pharmacist, in accordance with the conditions specified in this protocol. It is the Unblinded Pharmacist's responsibility to ensure that accurate records of study drug disposition and destruction are maintained.

### 5.2 Dosage, Preparation, and Administration

Study drug consists of NEOD001 or placebo. The NEOD001 dose is 24 mg/kg; however, the maximum dose administered is not to exceed 2500 mg. Therefore, subjects with a weight of 104.2 kg or greater will receive the maximum dose of 2500 mg. The subject's weight during Screening may be used for calculation of the first dose. Subsequent doses will be calculated based on the current weight at that visit. A change of  $\pm 10\%$  from the weight being used for dosing should trigger recalculation of the dose based on the new weight.

Each vial of 500 mg of NEOD001 will be reconstituted with 9.6 mL sterile WFI to a concentration of 50 mg/mL resulting in a buffered, isotonic, preservative-free solution with a total extractable volume of 10 mL. Study drug will be prepared in a 250 mL IV bag of 0.9% saline. The equivalent volume of reconstituted NEOD001 will be withdrawn prior to transferring the drug solution into the IV bag, such that the total IV bag volume will be 250 mL. A separate placebo will not be provided for this study. Subjects who receive placebo will be administered a

250 mL IV bag of 0.9% saline, which will look identical to the NEOD001 infusion bag. Refer to the Pharmacy Manual for complete information on preparing and administering the study drug.

One or two Unblinded Pharmacists or an appropriate designee (henceforth collectively referred to as the Unblinded Pharmacist) will be identified at each site who will be responsible for preparing the study drug; all other study team members must remain blinded to study drug assignment. The Unblinded Pharmacist will obtain the randomization number and treatment assignment information from the IVRS/IWRS, and will then prepare and reconstitute the study drug, providing it to the Investigator for administration. The Unblinded Pharmacist will maintain the records for drug accountability for audits or inspections.

The study drug should only be administered in settings where emergency resuscitative equipment and personnel trained in the management of anaphylaxis are immediately available to treat systemic reactions under the direct supervision of a physician.

Study drug will be administered as an initial 120 ( $\pm 10$ )-minute IV infusion on Month 1-Day 1. If, in the opinion of the Investigator, the subject tolerates the initial administration, subsequent infusions may be administered over 60 ( $\pm 10$ ) minutes once every 28 ( $\pm 5$ ) days; a minimum of 21 days between doses is required. Subjects may receive up to 12 infusions of study drug.

If there is concern about infusing 250 mL over 60 ( $\pm 10$ ) minutes in any specific subject, the length of the infusion may be extended over a longer period of time as clinically indicated. If the infusion must be extended beyond 4 hours, the study drug should be split into two 125-mL bags to ensure that the study drug will not remain at room temperature for longer than 4 hours (i.e., the second bag should remain refrigerated until ready for use). The volume contained in the administration tubing should be completely flushed using 30 mL of 0.9% Sodium Chloride Injection (USP) after administration of study drug. The infusion line should NOT be used for blood draws.

All subjects will be closely monitored for approximately 90 ( $\pm 10$ ) minutes after completion of the study drug infusion. The Investigator may increase this standard monitoring time if deemed appropriate or per local standards. In the event of any clinical concerns or suspicious signs or symptoms after the infusion, the subject will remain under observation for as long as the Investigator deems it appropriate.

## **5.3 Dosage Adjustments**

### **5.3.1 Withholding of Study Drug**

Subjects with symptomatic orthostatic hypotension and/or systolic BP <85 mmHg, which in the medical judgment of the Investigator would interfere with subject's ability to safely receive study drug, will have study drug withheld.

### **5.3.2 Management of Suspected Infusion-Related/Hypersensitivity Adverse Events**

In the event of a suspected infusion-related and/or hypersensitivity AE, the infusion should be immediately discontinued and appropriate supportive therapy should be administered per institutional practice, which may include, but is not limited to, epinephrine, IV fluids, corticosteroids, vasopressors, oxygen, bronchodilators, antihistamines, or acetaminophen/paracetamol. Subjects should be evaluated and carefully monitored until there is complete resolution of the AE or hypersensitivity signs and symptoms.

For subjects with a Grade 2 infusion-related AE, if it is appropriate to restart the infusion, it should be done at 50% of the original rate (i.e., if the initial infusion is administered over 120 minutes, the new rate should be based on administering 250 mL over at least 180 minutes). If the subject is to receive additional infusions in

subsequent weeks, the rate of these infusions should be discussed with and agreed upon prospectively by the Investigator and the Medical Monitor. In addition, for all subsequent infusions, maximal premedication must be administered according to institutional practice and should include an H1 blocker, an H2 blocker, an antipyretic such as acetaminophen/paracetamol and a steroid (e.g., 25-50 mg hydrocortisone IV).

If a subject experiences a Grade 3 infusion-related and/or hypersensitivity AE, the infusion should not be restarted. The decision to continue dosing this subject at their next scheduled administration should be discussed with the Medical Monitor. If the decision is made to proceed with subsequent dosing, **both** the dose and infusion rate will be reduced by 50% from the original dose and infusion rate. In addition, maximal premedication must be administered according to institutional practice and should include an H1 blocker, an H2 blocker, an antipyretic such as acetaminophen/paracetamol and a steroid (e.g., 25-50 mg hydrocortisone IV). Subjects who have an infusion-related and/or hypersensitivity AE at the subsequent scheduled study drug administration must have study drug permanently discontinued.

Subjects who experience a Grade 4 infusion-related and/or hypersensitivity AE must have study drug permanently discontinued.

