Number of Subjects and Cohort Specifications	50 subjects randomized to NEOD001 and 50 subjects randomized to placebo. The randomization will be stratified (Appendix 1) according to: 
 
• Complete response/very good partial response (CR/VGPR) vs partial response (PR) to most recent line of therapy
 
• Renal stages 1 or 2 vs renal stage 3
 

Study Drug, Dose, and Mode of Administration	
Study drug consists of NEOD001 24 mg/kg (dose not to exceed 2500 mg) or placebo.
 
Study drug will be administered once every 28 (<math>\pm</math>5) days; a minimum

	
of 21 days between doses is required. Subjects may receive up to 12 infusions of study drug.
 
Study drug will be administered in a 250 mL bag as an initial 120 (<math>\pm 10</math>)-minute intravenous (IV) infusion. If, in the opinion of the Investigator, the subject tolerates the initial infusion, subsequent infusions may be administered over 60 (<math>\pm 10</math>) minutes. The length of the infusion may be extended over a longer period of time if and when it is clinically indicated. If the infusion must be extended beyond 4 hours, the study drug should be split into two 125-mL bags to ensure that the study drug will not remain at room temperature for longer than 4 hours (i.e. the second bag should remain refrigerated until ready for use). If an infusion-related reaction occurs, follow instructions in Section 5.3.2.
 
Subjects should be closely monitored for 90 (<math>\pm 10</math>) minutes following completion of the study drug infusion. The Investigator may increase this standard monitoring time if deemed appropriate or per local standards. In the event of any clinical concerns or suspicious signs or symptoms after the infusion, the subject will remain under observation for as long as the Investigator deems it appropriate

Control Group	Normal saline will be used as the placebo control.

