Patients will receive monthly administrations of NEOD001 at 24 mg/kg (maximum 2500 mg) on day 1 of each month. The maximum planned number of infusions of NEOD001 is 12. With respect to NEOD001, there have been no hematologic side effects noted and infusion-related side effects are rare. To date, NEOD001 has been safe and well tolerated and its use is designed to optimize the potential for durable functional renal improvement. We will record vital signs and patient status before and after each administration of NEOD001 or placebo. NEOD001 or placebo will be given IV monthly. NEOD001 has been shown, in a phase I/II trial, to

improve the renal status of 60% of previously treated AL patients with renal involvement. There are no adjustments needed for renal function.

Hematologic and renal status will be evaluated every 3 months on study. Patients who have hematologic progression may stay on study through the 13-month active study period unless and until they begin chemotherapy for hematologic progression when they must come off study.

After completing 12 months of treatment and the confirmatory EOS visit, a subject may enter an OLE study during which subjects will receive active treatment with NEOD001 for 12 months and may receive concurrent chemotherapy.

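### Section 5.3.2 orders a Grade 2 restart at half the original infusion rate, but its worked example permits up to two thirds of that rate

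*Combined protocol and SAP*

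**What the plan says.** For a Grade 2 infusion-related reaction where a restart is judged appropriate, Section 5.3.2 states the rule as a percentage: "it should be done at 50% of the original rate". In the same sentence, introduced by i.e., it gives the rule as a volume and a time: "if the initial infusion is administered over 120 minutes, the new rate should be based on administering 250 mL over at least 180 minutes".

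The synopsis makes this section the working instruction for sites: "If an infusion-related reaction occurs, follow instructions in Section 5.3.2". Section 5.2 sets the bag volume at 250 mL and the first infusion at 120 (±10) minutes, with later infusions over 60 (±10) minutes if the first was tolerated. It also says: "Refer to the Pharmacy Manual for complete information on preparing and administering the study drug".

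No other part of the protocol gives a Grade 2 restart rate. For a Grade 3 reaction, Section 5.3.2 does not allow a restart. If dosing continues at the next visit, both dose and rate are cut by 50%, and no time example is given.

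**The concern.** An example introduced by i.e. restates the rule, so it should yield the same number. Here it does not. Staff setting a pump need a volume and a time, and the example is the part of the sentence that supplies them. A site that follows the percentage and a site that follows the example can both believe they are complying and still restart at different rates.

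The stake is patient safety. The subject has just reacted to an infusion that may contain a monoclonal antibody, and the more permissive figure is the faster one. Section 5.4 lists date, time and whether the dose was completely infused as the compliance record. It does not list rate, so a discrepancy might not be visible in the data.

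**Working it through.** **Inputs.** Volume 250 mL (Section 5.2). First infusion 120 minutes, window 110 to 130 (Section 5.2). Restart at 50% of the original rate, with an example floor of 180 minutes (Section 5.3.2).

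**Formula.** Rate = volume / time. At fixed volume, the new rate as a fraction of the original is the original time divided by the new time.

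**Trying to reproduce the plan's 180 minutes from its 50% rule**
- Original rate: 250/120 = 2.083 mL/min = 125 mL/h.
- Half of that: 62.5 mL/h (1.042 mL/min). Time for 250 mL: 240 minutes.
- Example floor: 250/180 = 1.389 mL/min = 83.3 mL/h.
- Fraction of original: 120/180 = 66.7%, a cut of 33.3% rather than 50%.
- Relative to the rule: 83.3/62.5 = 1.33, one third faster.

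The 180-minute figure is not reproduced. Any basis from 180 to just under 240 minutes meets the example and breaks the rule.

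**Other routes to 180**
- Fifty percent more time: 120 × 1.5 = 180. This lengthens the duration by half, which cuts the rate by only one third.
- Total infusing time when exactly half the bag has gone in: 60 + 120 = 180. The text bases the rate on the full 250 mL, not the remaining volume, and this works only for a reaction at the midpoint.
- Half the rate of a 90-minute infusion: 180/2 = 90. The example specifies 120.

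**Across the ±10-minute window.** The example is written for 120 minutes. If a site carried 180 minutes over unchanged:

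| Original infusion (min) | Time for 250 mL at half rate (min) | 180 min as % of original rate |
|---|---|---|
| 110 | 220 | 61.1% |
| 120 | 240 | 66.7% |
| 130 | 260 | 72.2% |

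**Effect at the bedside, 120-minute infusion.** For a reaction at minute *t*, the remaining volume takes 2(120 − *t*) minutes under the rule and 1.5(120 − *t*) at the example floor.

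| Reaction at (min) | Rule (min) | Example floor (min) | Finishes sooner by (min) |
|---|---|---|---|
| 30 | 180 | 135 | 45 |
| 60 | 120 | 90 | 30 |
| 90 | 60 | 45 | 15 |

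**Interaction with the 4-hour limit.** At half rate, total infusing time for an original duration *T* is *t* + 2(*T* − *t*) = 2*T* − *t*. With *T* = 120 and *t* = 30 this is 210 minutes, so a pause of more than 30 minutes passes 4 hours. With *T* = 130 and *t* = 15 it is 245 minutes before any pause.

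**The case against.** The best defence is that the percentage is explicit and can be followed. The 180 minutes is a minimum, and a 240-minute basis complies with the whole sentence. That is correct, and it means the sites are not under contradictory orders. It does not repair the example, which still permits rates that the rule excludes.

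The second defence is that little turns on it, and most of this stands:
- Section 1.1 says "infusion-related side effects are rare", and Section 1.3.1 reports no hypersensitivity reactions among 69 patients given 913 infusions in the Phase 1/2 study, as of an interim cut.
- The example covers only Grade 2 reactions restarted in a 120-minute infusion. Rates for subsequent infusions are agreed with the Medical Monitor, and about half of subjects in the blinded phase receive saline.
- Before a restart, "Subjects should be evaluated and carefully monitored until there is complete resolution of the AE". Section 5.2 requires resuscitation equipment and trained staff "immediately available to treat systemic reactions under the direct supervision of a physician", and about 90 minutes of observation afterwards.
- Even at the floor the infusion is slowed by a third. The routine later rate in subjects who tolerated the first infusion is 250 mL/h, although those are not subjects who have reacted.
- The documents contain no data comparing the safety of 67% and 50%.

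The Pharmacy Manual may already state the restart rate correctly. It was not available, so actual exposure at sites is unknown. The 61.1% to 72.2% range is hypothetical, because the protocol does not tell sites to use 180 minutes for other durations.

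The 4-hour limit is a fair practical objection to a longer infusion. The tension comes from the existing 50% rule, however, and correcting the example only makes it visible. These points bear on the size of the problem. None of them makes the example agree with the rule.

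**Conclusion.** The concern holds. The example in Section 5.3.2 does not express the 50% rule: for a 120-minute infusion it allows up to 83.3 mL/h against 62.5 mL/h, which is 66.7% against 50% of the original rate. Confidence in the mismatch is high, since it rests on one intact sentence and a division. Which figure was intended is not known. The 50% rate cut for Grade 3 in the same section hints at 50% but does not prove it.

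The practical reach is small, normally Month 1 of the blinded phase. The open-label extension in Appendix 11 also opens with a 120-minute infusion and gives no restart rate of its own, but it does not say that Section 5.3.2 applies, so extension to that phase is only a possibility. There is no effect on endpoint, population, sample size or analysis. It should be corrected because it is a wrong figure in an operative safety instruction.

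**What to change.** In Section 5.3.2, change the example to 250 mL over at least 240 minutes (twice the original duration). The words in parentheses also give the right answer for 110- to 130-minute infusions and for later 60-minute infusions, where half rate means 120 minutes. If the clinical team meant 180 minutes, keep it and change 50% to about 67%. The team has to choose; the protocol cannot settle it.

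Check that the Pharmacy Manual gives the same figure. Remind sites that the requirement in Section 5.2 to "ensure that the study drug will not remain at room temperature for longer than 4 hours" and its two-bag split still apply to a slowed infusion, counting any pause. Since a bag already hung cannot benefit from refrigerating a second one, the team may wish to say what to do with the remaining volume when 4 hours will be passed.

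The cost is one clause, a check of the manual and a notice to sites.
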